#### 14.3 Exploratory objectives

#### « Exploratory objectives 1, 2, 3 and 4 are stratifications to the co-primary objectives.»

- To estimate brand-specific CVE against hospitalisation due to laboratory-confirmed SARS-CoV-2 in severe acute respiratory infection (SARI) patients who have been vaccinated with at least 1 COVID-19 vaccine dose, compared to unvaccinated patients,
  - by severity level .
  - by calendar time .
- To estimate brand-specific CVE against hospitalisation due to laboratory-confirmed SARS-CoV-2 in SARI patients who completed a primary series vaccination, compared to unvaccinated patients,
  - by severity level .
  - by calendar time .
- 3. To estimate brand-specific CVE against hospitalisation due to laboratory-confirmed SARS-CoV-2 in SARI patients who previously completed a primary series with any COVID-19 vaccine and have received at least one additional COVID-19 vaccine dose , compared to (1) unvaccinated patients and to (2) patients who previously completed a primary series with any COVID-19 vaccine but who did not receive the last additional dose of interest ,
  - by severity level .
  - by calendar time .
- 4. [Only to support the interpretation of exploratory objective 3 ]: To estimate CVE across brands against hospitalisation due to laboratory-confirmed SARS-CoV-2 in SARI patients who previously completed at least a primary series with any COVID-19 vaccine but who did not receive the last additional dose of interest , compared to unvaccinated patients,
  - by severity level .
  - by calendar time .
- 5. To estimate the brand-specific effect of COVID-19 vaccination in patients who have [been vaccinated with at least 1 COVID-19 vaccine dose-- completed primary series vaccination] on length of hospital stay (in days) due to laboratory-confirmed SARS-CoV-2 admission compared with patients who [are unvaccinated have been vaccinated with at least 1 COVID-19 vaccine dose ...].
- 6. To study the potential occurrence of VAED by describing the clinical and laboratory features of critical COVID-19 disease  cases, by COVID-19 vaccine exposure status and time since vaccination. 

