 Throughout the protocol, additional dose refers to booster doses (1st, 2nd, 3rd...). COVID-19 vaccine dose will be classified as primary (P) or additional dose (N) by expert consensus.

 Patients who did not receive the last additional dose received one dose less (P+N-1) compared to the patients who received one additional dose of the vaccine of interest (P+N), further explanation can be found in section 15.14.4.

 The SARI patients used for the supporting objective are exactly the same patients as the ones used for the comparator groups of the supported objective.

 Only estimated if the type includes at least two brands or only the brand of interest.

 Three mutually exclusive categories: (a) hospital admission without intensive care unit (ICU) admission and without in-hospital death, (b) ICU admission without in hospital death and (c) in-hospital death.

 Calendar time at date of hospital admission as a proxy for changing genetic variants of the SARS-CoV-2 virus.

 The text between square brackets needs to be selected to match the exposure definitions from the co-primary objectives.

 Critical COVID-19 disease is defined as being admitted to ICU due to laboratory-confirmed SARS-CoV-2.

 It is postulated that the potential VAED risk may change with waning vaccine-induced immunity, hence with time since vaccination as a proxy.

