# **C VIDRIVE**

#### 15.9.2 Hospitalisation due to laboratory-confirmed SARS-CoV-2: level of severity

The following three mutually exclusive categories will characterise the severity of the hospitalisation due to laboratory-confirmed SARS-CoV-2 disease:

- 1. Hospital admission without ICU admission and without in-hospital death
- 2. ICU admission without in-hospital death
- 3. In-hospital death

COVID-19 hospitalisation that takes place within 3 months of the first COVID-19 hospitalisation will be considered as part of the same episode.

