#### 15.9.4 Critical COVID-19 disease

A critical COVID-19 disease case is defined as a COVID-19 disease case being admitted to the ICU. The clinical and laboratory characteristics of the critical COVID-19 disease cases will be described (Annex 1).

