#### 15.11.1.1 Primary vaccination

For the analysis of interest, the number of required COVID-19 cases to obtain precise estimates were obtained using a simulation-based sample size calculation. The simulation study reflects the design of the current study; a multi-site TNCC study with data from different sites combined using a metaanalytical approach (see Section 17.14 Data Analysis). Sample size calculations were performed with the number of equally sized sites being 10, the overall anticipated CVE being 80% or 90%, the control to case ratio being 3:1, 1:1 or 1:3, the overall vaccination coverage among controls being 60%, 80% or 90%, and the proportion of the vaccination coverage covered by the vaccine of interest being 10%, 25%, 50%, or 75%. For each combination of these parameters, the sample sizes for which the expected 95% CI range was ≤30% were obtained. The technical specifications of the sample size calculations are given in Appendix 6.

For various CVE, total vaccination coverages, and different proportions of the total vaccination coverage covered by the brand of interest, the number of COVID-19 cases required to meet the CI criterion are summarised in Table 4. Irrespective of the other considered parameter combinations, having at least 1,134 COVID-19 cases yields expected 95% CI ranges  $\leq$ 30%. The corresponding total number of SARI cases needed to be enrolled can be found in Table 5 and having at least 2,210 SARI cases yields expected 95% CI ranges  $\leq$ 30% for a control to case ratio of 1:1. As this sample size was obtained for the crude CVE instead of the adjusted CVE, it was decided to conservatively adjust the targeted sample size to 1.2 x 1,134 = 1,360 COVID-19 cases and 1.2 x 2,210 = 2,652 SARI cases.

Finally, in case the observed share of the different COVID-19 vaccine brands or the overall vaccination coverage rate observed in the study differs largely from the settings described, the sample size

**C** VIDRIVE

Version 4.0

calculations will be updated accordingly. The sample size might also be updated in case vaccine effectiveness estimates against specific COVID-19 genetic variants are required.

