# 15.14.4 Statistical analyses

# 15.14.4.1 Site-specific CVE

For every study site, the crude and confounder-adjusted brand-specific CVE against laboratoryconfirmed COVID-19 disease will be estimated as:

VE = (1 – OR) x 100%,

CINICRIVE

where *OR* denotes the crude or confounder-adjusted odds ratio, comparing the odds of vaccination among COVID-19-positive study participants to the odds of vaccination among COVID-19-negative study participants.

Confounder-adjusted CVE estimates will be derived from multivariable logistic regression models. The analysis to estimate brand-specific CVE will account for the differences in approved indications, discarding from the analysis patients for which the vaccine brand of interest is not indicated. All CVE estimates will be adjusted for calendar time.

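### Exploratory CVE by exclusive severity level mixes prevention of admission with movement between levels, and none of these estimates matches ICU-defined critical disease

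*Protocol*

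**What the plan says.** Section 15.9.2 sets the severity outcome: "The following three mutually exclusive categories will characterise the severity of the hospitalisation due to laboratory-confirmed SARS-CoV-2 disease". Level 1 is "Hospital admission without ICU admission and without in-hospital death", level 2 is "ICU admission without in-hospital death", and level 3 is in-hospital death. Section 15.5 lists the same levels. Footnote 5, in the abstract and in Section 14.3, attaches them to the CVE objectives: "Three mutually exclusive categories: (a) hospital admission without intensive care unit (ICU) admission and without in-hospital death", followed by the other two. Section 14.3 describes the rank of these analyses: "Exploratory objectives 1, 2, 3 and 4 are stratifications to the co-primary objectives".

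The effect measure in Section 15.14.4.1 is one minus an odds ratio, "comparing the odds of vaccination among COVID-19-positive study participants to the odds of vaccination among COVID-19-negative study participants". The protocol specifies no CVE for ICU admission regardless of survival, and none for ICU admission or death combined.

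For the description of possible vaccine-associated enhanced disease (VAED), Section 15.9.4 uses a different severe group: "A critical COVID-19 disease case is defined as a COVID-19 disease case being admitted to the ICU". That group includes ICU patients who later die.

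**The concern.** The level of a case is fixed by what happens in hospital, after vaccination. The protocol leaves open whether vaccination changes that course. Section 17 treats a milder course as unknown, exploratory objective 5 looks for an effect on length of stay, and Annex 1 considers the opposite possibility, enhanced disease.

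If the course does change, cases move between levels. A vaccinated patient who is spared the ICU leaves level 2 and adds to the vaccinated count in level 1. A vaccinated ICU patient who dies instead of surviving leaves level 2 and makes the vaccine look better there. The odds ratio at levels 1 and 2 therefore carries two effects that cannot be separated from that estimate alone.

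This matters because Annex 1 asks for CVE across severity levels and by time since vaccination in order to look for VAED. A reader will naturally take level 2 as effectiveness against ICU disease, and it is not. The critical cases described for VAED also have no matching effectiveness estimate.

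**Working it through.** **Inputs from the protocol.** Anticipated CVE is 80% or 90% for the primary series (Section 15.11.1.1). It is 70% for the comparator group, with relative CVE of 80% or 90%, for additional doses (Section 15.11.1.3). The protocol states no CVE by severity and no severity distribution, so there is no figure to reproduce.

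**Assumptions.** All test-negative controls are the reference at every level. Unvaccinated cases split 70/15/15% (ward only / ICU survivor / death). Vaccinated cases split 80/12/8%, 85/9/6% or 90/6/4%, all of which represent milder disease.

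**Formula.** With a common control group, the odds ratio at level k is (1 − overall CVE) × (share of vaccinated cases at k) ÷ (share of unvaccinated cases at k). CVE at k is one minus that. The nested version uses the share at level k or worse.

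**Level 1.** Example at overall CVE 80% with the 85/9/6 split: 1 − 0.20 × 0.85/0.70 = 75.7%, against 80% for any hospitalisation.

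| Overall CVE | Level 1, 80/12/8 | Level 1, 85/9/6 | Level 1, 90/6/4 |
|---|---|---|---|
| 90% | 88.6% | 87.9% | 87.1% |
| 80% | 77.1% | 75.7% | 74.3% |
| 70% | 65.7% | 63.6% | 61.4% |
| 20% | 8.6% | 2.9% | −2.9% |
| 10% | −2.9% | −9.3% | −15.7% |

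At 70% to 90% the gap runs from 1.4 points (90 − 88.6) to 8.6 points (70 − 61.4). Level 1 turns negative when overall CVE is below 1 − (unvaccinated share ÷ vaccinated share): 1 − 70/80 = 12.5%, 1 − 70/85 = 17.6%, 1 − 70/90 = 22.2%.

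**Floor at the planned values.** The vaccinated ward-only share cannot exceed 100%, so level 1 CVE cannot fall below 1 − (1 − CVE)/0.70. That is 85.7%, 71.4% and 57.1% at overall CVE of 90%, 80% and 70%. At 80%, a negative value would need fewer than 20% of unvaccinated cases to be ward only.

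**Opposite shift.** With vaccinated cases at 60/20/20% and CVE 80%, level 1 is 1 − 0.20 × 0.60/0.70 = 82.9%, now above 80%.

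**Level 2 against ICU admission.** Take case counts per group with equal exposure odds in controls, so no effect on admission is built in.
- Milder course: 28 unvaccinated ICU cases (20 survive, 8 die) and 14 vaccinated (12.6 survive, 1.4 die). Level 2 is 1 − 12.6/20 = 37%; CVE against ICU admission is 1 − 14/28 = 50%.
- Worse course: 28 ICU cases in each group, with deaths rising from 8 to 14. Level 2 is 1 − 14/20 = 30%; CVE against ICU admission is 1 − 28/28 = 0%.
- Multiplying the vaccinated counts by 0.20, to add a further 80% reduction, gives 1 − 2.52/20 = 87.4% against 90% in the first case and 1 − 2.8/20 = 86% against 80% in the second.

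**Level 3** is the top level, so the exclusive and nested versions are identical.

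**Match to critical disease.** Critical disease is ICU survivors plus ICU deaths. Level 2 omits the ICU deaths. Level 3 contains them but adds deaths outside the ICU. Levels 2 and 3 together also include deaths outside the ICU. No level or union of levels is defined as critical disease; levels 2 and 3 together would coincide with it only if every in-hospital death followed ICU admission.

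**The case against.** The other side has several sound points.

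- A reader might infer that the lower levels are simply understated. The documents do not support that: the direction depends on a milder course, which Section 17 calls unknown, and it reverses at level 1 under enhancement.
- A reader might infer that a protective vaccine would be reported with negative CVE. At the planned 70% to 90% this is nearly excluded. It needs overall CVE below roughly 12% to 22% on the splits tried. Waned or relative-CVE strata might be that low, but the protocol gives no such figure.
- The level 1 gap at the planned values is small beside the precision target for the main estimate, a 95% CI range of up to 30 points.
- Level 2 need not differ from a nested estimate. If ICU survival and death are reduced in the same proportion, for example 70/20/10% becoming 85/10/5%, level 2 CVE equals CVE against ICU or death.
- Low CVE at ward level with high CVE at ICU and death indicates attenuation, not VAED, when the levels are read together.
- Sections 15.9.2 and 15.9.4 do not contradict each other. Objective 6 is descriptive and calls for no CVE.
- The exclusive levels are a defined contrast. They mislead only if read as disease of at least that severity.
- The objectives are exploratory, sit in a template that study teams modify, and will be followed by an SAP.

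These points limit the size and direction of the problem but do not remove it. The protocol itself fixes the exclusive levels in several places. Level 2 can mislead in either direction on the question Annex 1 raises, and the estimate most readers would want for severe disease is not specified.

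**Conclusion.** The point holds as a modest, inexpensive improvement to an exploratory analysis. CVE at levels 1 and 2 is not effectiveness against disease of at least that severity whenever vaccination alters the hospital course in a way that changes the shares at those levels. On the assumed splits with milder disease, level 1 departs from CVE against any hospitalisation by about 1 to 9 points at overall CVE of 70% to 90%, and by more at low CVE. Level 2 departed from CVE against ICU admission by 13 points downwards (37% against 50%) and 30 points upwards (30% against 0%) with no added effect on admission, and by 2.6 and 6 points with a further 80% reduction. All these sizes rest on severity splits that are not in the protocol. Level 3 and the co-primary outcome are unaffected. The mismatch with critical disease needs no assumption about attenuation. A reader might also conclude that the exclusive levels should be reduced to description only; that is a preference, and nothing in the protocol requires it.

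**What to change.** In footnote 5 (abstract and Section 14.3), Section 15.5 and Section 15.9.2, add CVE for two nested outcomes: ICU admission regardless of survival, which matches Section 15.9.4, and ICU admission or in-hospital death. Compare each with all test-negative controls. Keep the three exclusive levels, and state that CVE at levels 1 and 2 is not CVE against disease of at least that severity.

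No new data are needed: the icu and death fields are already mandatory in Annex 4. The combined outcome also brings together severe events that the present levels split. The cost is a wording change and two more exploratory estimates per objective (for each comparator in objective 3).

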# 15.9.3 Hospitalisation due to laboratory-confirmed SARS-CoV-2: Length of hospital stay

Length of hospitalisation stay is defined as the number of overnights spent at the hospital from hospital admission till hospital discharge or death.

COVID-19 hospitalisation that takes place within 3 months of the first COVID-19 hospitalisation will be considered as part of the same episode. The length of stays of the admission will be summed.

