	virus2_ext	Laboratory result: In case of coinfectior second pathogen involved	Alternative to Q50 , when multiple pathogens are tested	Numeric (categorical)	0=No coinfection 1=SARS-CoV-2 2=Influenza 3=RSV 4=Pneumococcus 5=Other 9999=No information	х
	sequenced	Tested for genetic variants		Numeric (categorical)	0=No 1=Yes 9999=No information	
	variant_pangolin	Pangolin lineage name		Alfanumeric (categorical)	Example: B.1.117	
	EPI_ISL_nr	GISAID identification number		Alfanumeric	Example: EPI_ISL_412974	
ADDIT	IONAL HOSPITALISA	TION DATA	·	·		
	icu	ICU admission		Numeric (categorical)	0=No 1=Yes 9999=No information	х
	death	In-hospital death		Numeric (categorical)	0=No 1=Yes 9999=No information	х
	discharge_date	Date of discharge or death		DD/MM/YYYY	Date within the study period	Х
OTHE	R VACCINATIONS					
	fluvacc	Being vaccinated with at least one influenza vaccine within 12 months prior to SARI hospital admission		Numeric (categorical)	0=No 1=Yes 9999=No information	х
	fluvaccdate	Date of influenza vaccination		DD/MM/YYYY		Х
	pneumovacc	Received any pneumococcal vaccination	Any time	Numeric (categorical)	0=No 1=Yes 9999=No information	Х
	pneumovaccdate	Year of pneumococcal vaccination	Latest dose	YYYY		Х
TREA	TMENTS					

			COVIDRIV
pre_prophylaxis_6 mo	Having received anti-SARS-CoV-2 antibody products or other drugs indicated for pre-exposure prophylaxis for SARS-CoV-2 infection within 6 months prior to current hospitalisation	Binary	0=No 1=Yes 9999=No information
pre_prophylaxis_b rand	Brand of latest received anti-SARS-CoV- 2 antibody product or other drugs indicated for pre-exposure prophylaxis for SARS-CoV-2 infection	Numeric (categorical)	0=Kineret (anakinra)* 1=Regkirona (regdanvimab) 2=RoActemra (tocilizumab) 3=Ronapreve (casirivimab / imdevimab) 4=Veklury (remdesivir) 5=Xevudy (sotrovimab) 6=Evusheld (tixagevimab / cilgavimab) 7=Lagevrio (molnupiravir) 8=Paxlovid (PF-07321332 / ritonavir) 9=Other
pre_prophylaxis_d ate	Date of treatment start latest received anti-SARS-CoV-2 antibody product or other drugs indicated for pre-exposure prophylaxis for SARS-CoV-2 infection	DD/MM/YYYY	
post_prophylaxis_ 6mo	Having received anti-SARS-CoV-2 antibody products or other drugs indicated for post-exposure prophylaxis for SARS-CoV-2 infection within 6 months prior to current hospitalisation	Binary	0=No 1=Yes 9999=No information

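### Length of stay ends at discharge or death alike, so the vaccine comparison in exploratory objective 5 can be distorted, in either direction, by differences in in-hospital mortality

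*Protocol*

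**What the plan says.** Section 15.9.3 defines the outcome: "Length of hospitalisation stay is defined as the number of overnights spent at the hospital from hospital admission till hospital discharge or death". Readmissions for COVID-19 within 3 months belong to the same episode, and "The length of stays of the admission will be summed".

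Exploratory objective 5 (Abstract and section 14.3) uses this count for a comparison. It begins "To estimate the brand-specific effect of COVID-19 vaccination in patients who have" and names the outcome as "length of hospital stay (in days) due to laboratory-confirmed SARS-CoV-2 admission". Both the exposure and the comparator are bracketed options; the comparator may be unvaccinated patients or patients with at least one dose.

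Section 15.9.2 treats in-hospital death as a severity category of its own, and exploratory objectives 1 to 4 estimate effectiveness by those categories. Section 15.14.4 describes methods for odds ratios only, for example "Confounder-adjusted CVE estimates will be derived from multivariable logistic regression models". It states no model for length of stay and no rule for deaths in it.

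Annex 4 collects an admission date (`admissiondate`), an in-hospital death flag (`death`) and one end date (`discharge_date`), described as "Date of discharge or death". All three are mandatory, and the end date must lie within the study period.

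**The concern.** Death and live discharge are opposite outcomes, yet section 15.9.3 lets either one close the count in the same way. Section 15.9.2 keeps them apart; section 15.9.3 merges them. A difference in nights between exposure groups can then arise from differing mortality alone, or a real difference in time to going home can be hidden, reversed or inflated by it.

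The study cannot take equal mortality for granted, because it sets out to estimate effectiveness by severity, including in-hospital death, and to look for enhanced disease in vaccinated patients. The summing rule opens a second route: only patients discharged alive can add readmission nights.

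At stake is whether the result of objective 5 can be read as a vaccine effect on stay.

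**Working it through.** **Inputs.** The definition, the objective, the severity categories and the data fields come from the sections cited above. The protocol gives no in-hospital mortality by exposure, time to death, survivors' stay or target effect for length of stay. There is no planned figure to reproduce, and all numerical inputs below are assumptions.

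**Check 1: mean stay as a mixture.** Let p be in-hospital mortality, S survivors' mean nights and D mean nights to death. Then mean stay = (1 − p) × S + p × D. If S and D are the same in both groups, the difference (lower-mortality minus higher-mortality group) is (p_high − p_low) × (S − D).

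Take S = 12 in both groups and mortality 20% v 10%:

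| Nights to death | Mortality 20% | Mortality 10% | Difference |
|---|---|---|---|
| 5 | 0.8×12 + 0.2×5 = 10.6 | 0.9×12 + 0.1×5 = 11.3 | +0.7 |
| 7 | 0.8×12 + 0.2×7 = 11.0 | 0.9×12 + 0.1×7 = 11.5 | +0.5 |
| 12 | 12.0 | 12.0 | 0 |
| 16 | 0.8×12 + 0.2×16 = 12.8 | 0.9×12 + 0.1×16 = 12.4 | −0.4 |

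Other assumed values, with S = 10:
- Mortality 10% v 5%: 0.05 × (10 − 3) = +0.35 nights with deaths at 3 nights; 0.05 × (10 − 15) = −0.25 with deaths at 15.
- Mortality 30% v 10%: 0.20 × (10 − 3) = +1.4; 0.20 × (10 − 15) = −1.0.
- Equal mortality: 0 throughout.

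A real benefit can also be misread. Suppose vaccinated survivors stay 9 nights and unvaccinated survivors 10, with mortality 10% v 30%.
- Deaths at 3 nights: (0.9×9 + 0.1×3) − (0.7×10 + 0.3×3) = 8.4 − 7.9 = +0.5. The sign reverses.
- Deaths at 15 nights: (0.9×9 + 0.1×15) − (0.7×10 + 0.3×15) = 9.6 − 11.5 = −1.9. The one-night benefit is nearly doubled.

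**Check 2: competing hazards.** Assume a constant live-discharge hazard of 0.10 per night in both groups, and a death hazard of 0.025 unvaccinated, halved to 0.0125 by vaccination.
- In-hospital mortality: 0.025/0.125 = 20% v 0.0125/0.1125 = 11%.
- Mean nights to discharge or death: 1/0.125 = 8.0 v 1/0.1125 = 8.9. The vaccinated group looks 0.9 nights worse.
- Discharged alive by night 14: (0.10/0.125) × (1 − e^−1.75) = 66.1% v (0.10/0.1125) × (1 − e^−1.575) = 70.5%. More vaccinated patients go home.

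In this model deaths and discharges have the same mean time within each group, yet mean stay still differs. The cancellation at equal timing in Check 1 therefore depends on holding survivors' mean stay equal; here the discharge hazard is held equal instead. What counts as no effect on stay has to be stated.

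**The case against.** **Hospital use is a legitimate target.** The protocol never says that a short stay is favourable. For nights of hospital use, admission to discharge or death is the right count. That stands, and it is a reason to keep the count as a description. But objective 5 asks for an effect of vaccination on stay, and a difference that mortality alone can produce does not answer that.

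**This belongs to the SAP.** No model is stated, and a duration plus a death flag is what a competing-event analysis needs. The SAP could indeed repair the analysis. The outcome rule, however, is in the protocol, and as written it makes no distinction for deaths.

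**The stronger reading.** A reader might infer that early deaths score as favourable short stays, so that the estimate is biased against the vaccine. The documents do not support this. They give no time to death, and Check 1 changes sign when deaths come later than typical discharge. They do not say that mortality is expected to differ; section 17 says it is not yet known whether vaccination makes the disease milder. The comparator need not be unvaccinated patients.

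**Open stays are minor.** The Annex 4 date rule is a generic value check, and it affects only patients still in hospital at the end of a study expected to last two years. This stands; it needs an allowance, no more.

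**Death is reported elsewhere.** In-hospital death has its own severity category. That helps interpretation but does not separate it from stay in objective 5.

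**Conclusion.** The point holds as a conditional one. Section 15.9.3 closes a stay at death as at discharge, and objective 5 compares that count by vaccine exposure. If in-hospital mortality or time to death differs by exposure, the comparison can be distorted either way. With survivors' mean stay equal, the lower-mortality group looks longer if deaths precede typical discharge and shorter if they follow it; mean stay is undistorted if the timing is equal.

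Under the assumed inputs with no true effect on survivors' stay, Check 1 runs from −1.0 to +1.4 nights. These figures illustrate the mechanism; they do not predict this study's result. The weight is moderate: one exploratory objective in a template whose objectives are selected by the study team, with no co-primary or secondary estimate affected. It is worth correcting because the correction is cheap.

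**What to change.** For objective 5, in sections 15.9.3 and 14.3:

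- Analyse time from admission to discharge alive, with in-hospital death as a competing event, and censor stays still open at data cut-off. State whether the effect is read from the cumulative incidence of live discharge or from the cause-specific hazard. As Check 2 shows, the first also responds to mortality (66.1% v 70.5%), while the second is equal in the two groups by construction.
- Report in-hospital death by exposure beside it.
- Keep total nights to discharge or death as a descriptive measure of hospital use only.
- State how summed readmissions within 3 months enter, including live discharge followed by death on readmission. One workable choice is to base the time-to-event analysis on the index admission and report summed nights descriptively.
- In Annex 4, allow for a stay still open at cut-off in the rule for `discharge_date`.

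The cost is a short amendment to section 15.9.3 and the Annex 4 rule, and a slightly more complex model for one exploratory objective. For an index-admission analysis, `admissiondate`, `death` and `discharge_date` suffice, so no new variable is needed.
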